## 7.1.7 Drug Accountability

The investigator/institution is responsible for IMP accountability, reconciliation, and record maintenance (i.e., receipt, reconciliation, and final disposition records).

During the study, all IMP vials will be reconciled against the current inventory and the dispensing records as a component of the monitoring visits.

IMP administration data kept at the site will be monitored throughout the study by the monitor. After completion of the study, copies of all records regarding the IMP will be provided to the sponsor, who will decide on the return or destruction of any unused IMP.

If any unused IMP should be destroyed at the site (according to institutional policies, copies of which must be supplied to the sponsor or sponsor's designee before destruction takes place, and in compliance with the current applicable regulatory requirements) after drug accountability has been assessed by the study monitor, this destruction must be documented. If unused IMP cannot be destroyed at the site, it needs to be returned to the depot.

## 7.1.8 Treatment Compliance

If a subject misses a visit or a subject appears at the study center for a scheduled infusion but the infusion cannot be administered for any reason, the visit can be repeated within 3 days and the infusion given. Otherwise, the infusion will be considered as omitted and documented accordingly in the CRF.

InflaRx	Clinical Study Protocol,
	Version 4.0 Including Amendment 02, 14 May 2020
IFX-1	IFX-1-P2.7

Subjects who omit more than 2 scheduled (consecutive or non-consecutive) infusions will be discontinued from the study and will undergo the End of Treatment visit (Visit V16) and the 2 observation visits.

## 7.1.9 Overdose of IMP

At least 48 hours must have elapsed between each dose of IFX-1. Visits should be scheduled appropriately. Any second administration within this time, or any administration that is greater than the scheduled dose will be considered an overdose. The consequences of an overdose with IFX-1 are not known. InflaRx does not recommend specific treatment in case of an overdose.

Overdoses must be recorded as TEAEs.

In the event of an overdose, the investigator/treating physician should:

- 1. Contact the sponsor or sponsor's designee immediately.
- 2. Closely monitor the subject for any adverse events or SAEs and laboratory abnormalities for at least 7 days. If more than 130% of the dose is given, the patient should be kept in hospital overnight.
- 3. Obtain a plasma sample for IFX-1 concentrations if requested by the sponsor or sponsor's designee (determined on a case-by-case basis).
- 4. Document the quantity of the excess dose of the overdose in the CRF.
- 5. If there are any symptoms, treatment should be initiated as deemed medically appropriate by the investigator.

Decisions regarding dose interruptions or modifications will be made by the investigator in consultation with the sponsor or sponsor's designee based on the clinical evaluation of the subject.

## 7.2 **Prior and Concomitant Therapy and Procedures**

## 7.2.1 Recording of prior and concomitant therapy and procedures

Any medication or vaccine (including procures such as laser- or photo-therapy, over-thecounter or prescription medicines, vitamins, and/or herbal supplements) that the subject has used in the 3 months, or biologicals (see 81 for Prohibited Biologics) used within 12 months, before screening, is receiving at the time of screening, or receives during the study must be recorded in the source data and CRF along with:

- Reason for use
- Dates of administration including start and end dates
- Dosage information including dose, frequency, and route of administration

InflaRx	Clinical Study Protocol,
	Version 4.0 Including Amendment 02, 14 May 2020
IFX-1	IFX-1-P2.7

The sponsor or sponsor's designee should be contacted if there are any questions regarding concomitant or prior therapy.

## 7.2.2 Allowed Concomitant Therapy

#### Wound care for pyoderma gangrenosum

Wound care is performed at the scheduled visits, and 2 to 3 times a week depending on necessity according to the standard of care.

Further details of wound care are given in 82.

Concomitant use of wound care dressings on pyoderma gangrenosum ulcers is permitted with absorptive dressings, with or without antiseptics. However, the allowed antiseptics are limited (see 82). No topical therapy is allowed. Standard compression therapy throughout the study is required (Shavit and Alavi 2019).

#### Antibiotic therapy for pyoderma gangrenosum

Oral antibiotic therapy for treatment of superinfection of pyoderma gangrenosum wounds is permitted.

#### Analgesic therapy for pyoderma gangrenosum

Short-acting opioid or non-opioid analgesic therapy may be initiated at any time during the study. If possible, analgesic therapy should be avoided on the day of pain assessments until the assessments are made.

Subjects will be required to report any analgesics that are taken. All use of analgesics and any dose adjustments will be recorded in the source documentation and in the CRF.

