# **Objectives and Endpoints:**

Objectives	Endpoints
Primary	
• Explore the safety of IFX-1 for the treatment of subjects with pyoderma gangrenosum	• Occurrence, nature and intensity of treatment emergent adverse events (TEAEs), related TEAEs, serious TEAEs, and adverse events of special interest
Key Secondary	
• Explore the efficacy of IFX-1 for the treatment of pyoderma gangrenosum	
 
Responder rate defined as Physician's Global Assessment ≤3 of target ulcer at Visits V4, V6, V10, and V16 (End of Treatment [EOT])
 
Time to complete closure of pyoderma
 

	gangrenosum target ulcer (investigator assessment)
• Explore additional clinical outcome parameters in subjects with pyoderma gangrenosum under the treatment with IFX-1	• Percentage change in wound area and wound volume (wound healing) of target ulcer between Visits V1-V4, V1-V6, V6-V10; V10-V16, and V1-V16 (photographic assessment)
	• Rate of change per day in area of target ulcer (photographic assessment)
	• Number of subjects with a decrease in area of target ulcer of 50% or more at Visit V16 (EOT) compared to baseline (photographic assessment)
	• Number of subjects with a decrease in area of target ulcer of 100% at Visit V16 (EOT) compared to baseline (remission) (photographic assessment)
	• Degree of erythema and border elevation of the target ulcer compared to baseline at Visits V4, V6, V10, and V16 (EOT) (investigator assessment)
	• Mean change from baseline in pain assessed by Numeric Rating Scale (NRS) at Visits V4, V6, V10, and V16 (EOT)
	• Mean change from baseline in Dermatology Life Quality Index (DLQI) at Visits V4, V6, V10, and V16 (EOT)

InflaRx	Clinical Study Protocol,
	Version 4.0 Including Amendment 02, 14 May 2020
IFX-1	IFX-1-P2.7

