## 7.2.3 **Prohibited Therapy**

The following therapies are prohibited for all subjects from screening until Visit EOT or discontinuation from the study:

- Subject has received a live attenuated vaccine within 3 months prior to screening or plans to receive a live attenuated vaccine during the study or up to 4 weeks after the last study product administration.
- New therapy with biologicals (see 81 for Prohibited Biologics). Biologicals used for an underlying disease at a stable dose may be continued
- Any other systemic medication for pyoderma gangrenosum, including, but not limited to methotrexate, cyclosporine, retinoids, and fumaric acid esters
- Oral or injectable corticosteroids (more than 10 mg prednisone or prednisone equivalent)

- Non-stable, chronic use of high dose oral opioid analgesics
- New prescription topical therapies for pyoderma gangrenosum
- Over-the-counter topical antiseptic washes, creams, ointments, gels, and liquids containing antibacterial agents to treat pyoderma gangrenosum

The following is prohibited for all subjects from screening until Visit Ob2 or discontinuation from the study:

• Any investigational agent

The investigator should contact the sponsor or sponsor's designee if there are any questions regarding prior or concomitant therapy.

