# 9.3.4 Numeric Rating Scale for Pain

The numerical rating scale (NRS) is perhaps the most common pain assessment tool used. It is an 11-point scale (from 0 represent no pain to 10 representing the worst pain the subject can imagine). Subjects are asked to rate the intensity of their pain "right now" verbally with a number. The value is recorded in the CRF. The validity of the NRS has been well established and it has been shown to be easy to use.

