## 10.3.3 Pain and Quality of Life Analyses

Pain will be assessed by a:

• NRS at Screening, and Visits V1, V4, V6, V10, V16 (EOT), and Ob2

and quality of life by the:

• Dermatology Life Quality Index score at Screening, and Visits V1, V4, V6, V10, V16 (EOT), and Ob2

Basic descriptive statistics (e.g., number of observations (n), mean, standard deviation, minimum, median, maximum, lower quartile, upper quartile) will be displayed for the absolute values by visit and for the change of baseline at each visit for each scale.

The number and percentage of subjects in each answer category will be displayed for each of the 10 Dermatology life quality index items.

All analyses will be conducted on the SAF. Analyses will generally be performed for the entire SAF as well as the 3 dosing groups separately. Additional stratifications based on actual dosing and IMP compliance will be defined in the statistical analysis plan.

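### The pain analysis ignores the recorded analgesic use, so new or increased analgesia can look like improvement on IFX-1 and reduced analgesia can hide one

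*Combined protocol and SAP*

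**What the plan says.** The synopsis (Objectives and Endpoints) lists mean change from baseline in the pain NRS at V4, V6, V10 and V16 among the additional clinical outcomes under IFX-1. Section 9.3.4 defines the instrument as an 11-point scale: "Subjects are asked to rate the intensity of their pain" at the moment of asking, given verbally as a number.

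On analgesics, section 7.2.2 states: "Short-acting opioid or non-opioid analgesic therapy may be initiated at any time during the study". It continues: "If possible, analgesic therapy should be avoided on the day of pain assessments until the assessments are made". No minimum interval is given. Section 7.2.3 prohibits a narrow class: "Non-stable, chronic use of high dose oral opioid analgesics". Section 7.2.2 also requires a full record: "All use of analgesics and any dose adjustments will be recorded in the source documentation and in the CRF". Under section 7.2.1 that record covers reason, start and end dates, dose, frequency and route; clock time is not listed.

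For the analysis, section 10.3.3 provides descriptive statistics that "will be displayed for the absolute values by visit and for the change of baseline at each visit for each scale". These are produced on the safety set (SAF), overall and by dosing group. The only further stratifications announced are actual dosing and IMP compliance. Section 10.3 defers the handling of missing, unused and spurious data to a separate SAP. Section 7.1.4 confirms that the study is open label and not randomised.

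**The concern.** A rating of current pain responds to a recent analgesic dose. The protocol allows such a dose to be introduced after baseline, asks for it to be withheld before the rating only where feasible, records it, and then does not use the record in the pain analysis. There is no comparator in which the same analgesic use would occur and cancel out. A mean change at V10 or V16 could therefore combine a drug effect, an analgesic effect and the natural course of the disease, and the planned table gives no way to see how much is analgesia.

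New use is foreseeable. The rationale for Amendment 02 (Appendix 8) describes the pain of these ulcers as debilitating and says the patients need strong relief. The same amendment revised the analgesic rules, but its list of changes shows no matching change to the pain analysis.

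At stake is what the study may say about pain on IFX-1. In an exploratory study the described mean is the result. Calling it descriptive removes significance claims but does not remove bias.

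**Working it through.** **No planned figure to reproduce.** The protocol gives no sample size calculation, no assumed pain effect and no standard deviation. The check is therefore a comparison of the text, followed by an illustration.

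**Which patterns of use affect the change from V1**

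| Analgesic use at the visit relative to V1 | Effect on NRS change |
|---|---|
| None at either | None |
| Unchanged | Present in both ratings, so no bias in the change by itself |
| New or increased, rating taken under drug effect | Change looks more favourable |
| New or increased, dose effectively withheld before the rating | Little or none |
| Reduced | Change looks less favourable |

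The protocol allows every row, and section 10.3.3 pools them.

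**Size, illustration only.** Let k of n subjects in a group start an analgesic after V1, and let each rate d points lower because of it, with no IFX-1 effect on pain. The group mean change then shifts by (k/n) × d in the direction of improvement. The group size n = 6 comes from section 7.1.2. Both k and d are assumptions, because the documents give neither.

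| Starters among 6 | d = 1 | d = 2 | d = 3 |
|---|---|---|---|
| 1 | 1/6 × 1 = 0.17 | 0.33 | 0.50 |
| 2 | 0.33 | 2/6 × 2 = 0.67 | 1.00 |
| 3 | 0.50 | 1.00 | 3/6 × 3 = 1.50 |

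For all 18 subjects, 3 starters give 0.17, 0.33 and 0.50, and 6 starters give 0.33, 0.67 and 1.00.

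**Withholding.** If a share w of the affected ratings is taken free of drug effect, the shift becomes (k/n) × d × (1 − w). With w = 0.5, also an assumption, the range for a group of 6 halves to about 0.08 (1/6 × 1 × 0.5) up to 0.75 (3/6 × 3 × 0.5).

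**Opposite direction.** A subject who cuts down after V1 and rates d points higher as a result moves the mean of a group of 6 by d/6 towards worsening. One such subject with d = 2 gives 2/6 = 0.33.

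**Choice of sensitivity rule.** Replacing an affected rating with the V1 value alone would be unsafe. Take V1 = 6 and a rating of 8 despite a new analgesic. The change of +2 would become 0, a recorded worsening would vanish, and the mean of a group of 6 would move by 2/6 = 0.33 in favour of IFX-1. Taking the worse of V1 and observed keeps the 8. With V1 = 6 and an observed 4, the same rule gives 6, which is no improvement.

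**The case against.** The case against is substantial, and several parts of it stand.

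- **Mitigation exists.** New opioids are limited to short-acting ones, and sites are asked to hold analgesics until the rating is done. For a rating of current pain this is a real protection. It is incomplete, because it is conditional, has no stated interval, and section 7.2.1 does not ask for the time of a dose.
- **The direction is not fixed.** A reader might infer that opioid use will necessarily be counted as an IFX-1 benefit. The documents do not support that. The bias needs a rating under drug effect, and analgesics used at V1 and reduced as ulcers heal would work against IFX-1.
- **Stable opioids.** A reader might also infer that patients on permitted stable opioids bias the endpoint. Unchanged use is present in both ratings and does not by itself create a change.
- **The separate SAP.** Section 10.3 calls itself a summary and points to a SAP that is not in the text reviewed. The omission is shown for the protocol only. Section 10.3.3 does say which stratifications that SAP will add for pain, and analgesic use is not among them.
- **Limited consequence.** Pain is one of several descriptive secondary outcomes. It plays no part in the interim analyses (10.3.6), the dose increase at V7 (7.1.2) or the decision to open the next group (9.4.9). Ulcer area and the Physician's Global Assessment are collected at the same visits, so a fall in pain without ulcer response would be noticed. An as-observed mean, regardless of concomitant medication, is a legitimate summary.

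These points limit the size and certainty of the problem. They do not explain why the collected analgesic record should stay out of the pain analysis.

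**Conclusion.** The point holds in a limited form. As the protocol stands, the NRS summary can mix analgesic effect with any effect of IFX-1, in either direction, and the planned output would not show it. The 0.17 to 1.5 point range for a group of 6 rests entirely on assumed numbers of starters and assumed drops. Its upper end needs half the group to start an analgesic and each to fall by 3 points, with no effective withholding. It shows how easily a mean of six can move; it does not predict that it will.

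One further reading goes beyond what is established: that the Dermatology Life Quality Index is distorted to the same degree. Section 9.3.3 does include a question on soreness and pain over the last week, which same-day withholding cannot protect. But that question contributes at most 3 of 30 points, so the conclusion here is confined to the NRS.

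The primary safety objective and the wound endpoints are unaffected. The change is worth making because it is cheap, uses data largely collected already, and determines whether a statement about pain can be interpreted.

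**What to change.** In section 10.3.3, and in the SAP before database lock, keep the as-observed mean NRS change and add:

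1. **A split by analgesic use.** Show NRS change by visit according to use of any analgesic, opioid or non-opioid, relative to V1: none, unchanged, reduced, new or increased. Write down in advance how mixed changes are classified.
2. **A sensitivity table.** At any visit with new or increased analgesia, set the rating to the worse of the V1 and observed values, so that apparent improvement is not credited and worsening is kept. This is a cautious bound, not an estimate of pain without analgesics. It does not address reduced use, which the split shows.
3. **One yes/no item on the NRS page**, including at V1: was an analgesic taken before the rating that day?

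Base any statement about pain on both tables, read beside the as-observed mean. The clinical rule on analgesics is not changed.

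The cost is one or two descriptive tables, one CRF item, small cells in groups of 6, and possibly a less favourable pain figure.

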## 7.2.3 **Prohibited Therapy**

The following therapies are prohibited for all subjects from screening until Visit EOT or discontinuation from the study:

- Subject has received a live attenuated vaccine within 3 months prior to screening or plans to receive a live attenuated vaccine during the study or up to 4 weeks after the last study product administration.
- New therapy with biologicals (see 81 for Prohibited Biologics). Biologicals used for an underlying disease at a stable dose may be continued
- Any other systemic medication for pyoderma gangrenosum, including, but not limited to methotrexate, cyclosporine, retinoids, and fumaric acid esters
- Oral or injectable corticosteroids (more than 10 mg prednisone or prednisone equivalent)

- Non-stable, chronic use of high dose oral opioid analgesics
- New prescription topical therapies for pyoderma gangrenosum
- Over-the-counter topical antiseptic washes, creams, ointments, gels, and liquids containing antibacterial agents to treat pyoderma gangrenosum

The following is prohibited for all subjects from screening until Visit Ob2 or discontinuation from the study:

• Any investigational agent

The investigator should contact the sponsor or sponsor's designee if there are any questions regarding prior or concomitant therapy.

## 7.3 Treatment After the End of the Study

No treatment with IFX-1 is foreseen after Visit EOT. The further treatment of the pyoderma gangrenosum is at the discretion of the investigator.

# 8 DISCONTINUATION/WITHDRAWAL CRITERIA

Each early discontinuation of individual subject participation, irrespective of the reason for discontinuation, must be documented by the investigator. If possible, the date, circumstances, and reason for discontinuation should be documented.

The investigator will attempt to complete all procedures usually required for Visit EOT for subjects discontinuing. See the Schedule of Assessments (Section 2) for data to be collected at the time of study discontinuation and follow-up and for any further evaluations that need to be completed.

## 8.1 Discontinuation of the Study

The study may be discontinued by the sponsor at any site if any of the following criteria are met:

- The study protocol is not adequately adhered to (protocol violations) despite training of the study site personnel
- The data quality is deficient
- The recruitment is inadequate

Additionally, the entire study can be discontinued at all sites by the sponsor at any time for medical or ethical reasons.

The investigator(s) will be notified in writing, outlining the reasons for discontinuation, and the investigator(s) must promptly inform all participating subjects. Detailed instructions on further assessments will be provided.

InflaRx	Clinical Study Protocol,
	Version 4.0 Including Amendment 02, 14 May 2020
IFX-1	IFX-1-P2.7

All study materials, except documents needed for archiving requirements, will be returned to the sponsor, including all records regarding the IMP, and the sponsor will decide on whether any unused IMP should be returned or destroyed. The sponsor or sponsor's designee will ensure that any outstanding data clarification issues and queries are resolved and that all study records at the study site are complete.

In accordance with applicable regulatory requirements, the sponsor or sponsor's designee will promptly inform the competent regulatory authorities of the discontinuation and its reason(s), and the investigator or sponsor or sponsor's designee will promptly inform the IRB.

The approval of the study can be rescinded, or the study can be discontinued by a competent authority or a responsible IRB.

# 8.2 Discontinuation of the IMP

Subjects must be discontinued from treatment with the IMP because of:

- Unacceptable toxicity or TEAE, as determined by the investigator
- Anaphylactic or other serious allergic reaction
- Serious infection, including meningitis and sepsis
- If, in the investigator's opinion, continued administration of IMP could be detrimental to the subject's well-being
- Use of prohibited treatment that in the opinion of the investigator or sponsor or sponsor's designee necessitates the subject being removed
- Biopsy confirmation of any malignancy
- Pregnancy
- Abnormal liver function meeting Hy's Law criteria (62).

# 8.3 Withdrawal from the Study

A subject may withdraw from the study at any time at his/her own request or may be withdrawn at any time at the discretion of the investigator for safety, behavioral, compliance, or administrative reasons.

Subjects may withdraw their consent at any time without giving reasons. Nevertheless, they should be asked about the reason(s) for discontinuation after being informed that they do not need to do so. Information as to when they withdrew consent must be documented.

If the subject withdraws consent for disclosure of future information, the sponsor may retain and continue to use any data collected before such a withdrawal of consent.

If a subject withdraws from the study, he/she may request destruction of any samples taken and not tested, and the investigator must document this in the source data.

# 8.4 Lost to Follow-Up

A subject will be considered lost to follow-up if he or she repeatedly fails to return for scheduled visits and is unable to be contacted by the study site. The date of being lost to follow-up is defined as the last date with any assessment of the subject.

The following actions must be taken if a subject fails to return to the study site for a required study visit:

- The site must attempt to contact the subject and reschedule the missed visit as soon as possible and counsel the subject on the importance of maintaining the assigned visit schedule and ascertain whether or not the subject wishes to and/or should continue in the study.
- Before a subject is deemed lost to follow up, the investigator or designee must make every effort to regain contact with the subject (e.g., 3 telephone calls at 3 different times on consecutive days or local equivalent methods). These contact attempts should be documented in the subject's medical record.
- Should the subject continue to be unreachable, he/she will be considered to have withdrawn from the study with a primary reason of lost to follow-up.

